7 STUDY DESIGN

7.1 Endpoints

7.1.1 Primary Endpoints:

- The safety and tolerability of LAU-7b will be assessed in all patients through the performance of physical examinations, vital signs, ECG, safety laboratory tests, and adverse events reporting, compared to placebo treated patients;
- The absolute change in FEV₁ percent predicted at the Day 161 visit (24 weeks) relative to pre-study values, LAU-7b compared to placebo treated patients.

7.1.2 Justification for the Primary Endpoints

Primary Efficacy Endpoint: Fenretinide is proposed as an anti-inflammatory therapy with the ability to normalize plasma AA/DHA ratio, and in pre-clinical work, reduce *Pseudomonas* burden. Chronic lung inflammation and infection are at core of the lung destruction over time. Along with safety, it is therefore most relevant to assess the effect of correction of the lipidomic abnormality on FEV₁, a clinically meaningful outcome in CF and the most characterized index for assessing lung function in CF. If indeed fenretinide has positive effects on the immune-inflammatory response, on the function of CFTR and exert anti-infective effect against *PsA*, this will result in a positive absolute difference in the lung function relative to placebo-treated patients, an effect that should be observed over the 6-months duration of the study. Other variables susceptible to be positively affected by an anti-inflammatory and pro-resolving therapy will be evaluated as secondary endpoints.

Safety as a Primary Endpoint: In the proposed study, due to the longer duration of treatment in CF patient, relative to the previous Phase Ib and the increased sample size, these are relevant reasons for nominating safety as a co-primary endpoint, along with assessing efficacy. Similar to the previous study, safety will be assessed during and after the study, taking the screening and baseline status of the patients as a reference. In addition, particular attention will be put on objectively investigating reported symptoms of nyctalopia and/or dermatological disorders, the latter being known class effect of retinoids (including vitamin A). Fenretinide has a very good safety record in other indications at doses superior to the one evaluated in this study, and was shown to be well tolerated in the Phase Ib study with only few adverse events deemed related to the study drug. Still, by administering the study drug over a longer period of time, it is necessary to err on the safe side and continue to build a comprehensive safety database on fenretinide in CF.

7.1.3 Secondary Endpoints

- The proportion of patients achieving normalization of AA, DHA and the AA/DHA ratio in plasma phospholipids, LAU-7b compared to placebo. In this study, the normalization means a value or ratio value reaching the mean observed in healthy controls ± 1 SD;
- The absolute and relative (%) change from pre-study in FEV₁ percent predicted on Days 21, 49, 77, 105 and 189 visits (3, 7, 11 and 15 weeks during treatment and approximately 4 weeks after treatment, respectively), as well as the relative (%) change in FEV₁ % predicted on Day 161 (24 weeks), LAU-7b compared to placebo;
- The effect on the time to first protocol-defined PEx, LAU-7b compared to placebo;
- The effect on the incidence of protocol-defined PEx, LAU-7b compared to placebo;
- The effect on the time to first antibiotic use (other than chronic inhaled antibiotics already started prior to trial or oral chronic azithromycin), LAU-7b compared to placebo;

- The effect on the number of antibiotic treatments (other than chronic inhaled antibiotics already started prior to trial or oral chronic azithromycin), LAU-7b compared to placebo;
- The effect on the number of days of antibiotic treatment (other than chronic inhaled antibiotics already started prior to trial or oral chronic azithromycin), LAU-7b compared to placebo;
- The change from pre-study in systemic markers of inflammation in whole blood (total white cell count and absolute neutrophil count), serum (hsCRP and serum amyloid A), and plasma (calprotectin, haptoglobin, IL-1ra, IL-6, IL-8 IL-10, G-CSF, ceruloplasmin and neutrophil elastase antiprotease complexes), LAU-7b compared to placebo;
- The changes from pre-study in body weight and BMI, LAU-7b compared to placebo;
- The overall change in the *PsA* density in the sputum, from baseline through 12 and 24 weeks of treatment, when measured by the difference in the Area Under the Curve (AUC) of the CFU, LAU-7b compared to placebo;
- The fenretinide steady-state pharmacokinetics, depicted by C_{min} plasma concentrations at the end of the first and sixth treatment cycle;
- To assess the impact on overall health, daily life, perceived well-being and symptoms measured with the CFQ-R (total and respiratory domain) from pre-study to 12 and 24 weeks, LAU-7b compared to placebo.

7.1.4 Exploratory Endpoints

- The change from pre-study in AA, DHA and EPA in phospholipids and metabolipidomic markers (eicosanoids and docosanoids), LAU-7b compared to placebo;
- The change from pre-study in plasma oxidative stress makers (malondialdehyde, nitrotyrosine), LAU-7b compared to placebo;
- The changes from pre-study of in plasma ceramide subclass concentrations, LAU-7b compared to placebo;
- The change in plasma lipidomics (AA, DHA, AA/DHA ratio and EPA), inflammation markers, plasma oxidative stress markers, FEV₁, body weight and BMI measurements, between the start and the end of IV-treated PEx (performed only in patients who receive IV antibiotics for what their treating physician considers an exacerbation), LAU-7b compared to placebo;
- The change from pre-study in systemic bone formation/resorption markers, LAU-7b compared to placebo;
- At specific clinical sites, the change in bone density from baseline through 24 weeks of treatment, LAU-7b compared to placebo;
- At specific clinical sites, the changes in clinical scoring using the Matouk Disease Score contrasting the post-treatment score to the pre-study score, LAU-7b compared to placebo;
- Correlation of plasma retinol and retinol-binding protein levels measured during the study with ophthalmological assessments.

7.2 Study Overview

7.2.1 Description

APPLAUD is an international, multicentre, randomized, double-blind (patients, Investigators and blinded study staff), placebo controlled Phase II study of LAU-7b for the treatment of CF through its effect on the CF-linked AA/DHA imbalance.

To be eligible for the study, patients must have a diagnosis of CF, be aged 18 years and above, have undergone at least one IV antibiotic-treated PEx in the year prior and meet all other study inclusion and exclusion criteria at screening.

Eligible patients will be randomized 1:1, after stratification for 1- baseline FEV₁, 2- PEx number in prior year, and 3- Co-administration or not of Kalydeco®, Orkambi®, Symdeko® or another commercially available CFTR modulator product, to either LAU-7b (active) group or placebo (control) group. After randomization, patients will enter the treatment phase of the study. There will be no active control treatment but patients will undergo the CF Standard of Care at their institution.

A minimum of 136 patients will be recruited and randomized for the treatment phase of the study in the expectation that at least 120 patients complete the study as per protocol. Patients will be enrolled at approximately 35-40 centers in the United States of America, Canada and Australia, possibly in Europe. The study treatment (LAU-7b or matching placebo) will be administered in the fed state with the first meal of the day (morning if possible) for cycles consisting of 21 days on treatment followed by a 7-day treatment-free period.

Patients will be evaluated at pre-specified times during and after the study treatment period, for safety, efficacy, pharmacodynamics and pharmacokinetics, as well as Quality of Life. Patients undergoing PEx during the study will also be subjected to PEx-related assessments prior to- and after the therapeutic antibiotic course if the PEx severity meets the criteria for IV antibiotic treatment.

This design is appropriate for this phase of development and will ensure that the highest quality of data is collected with minimal bias and the patient’s safety and wellbeing are preserved. A Data and Safety Monitoring Board (DSMB) will be created for this study.

The overall study structure is presented below in Figure 5.

[figure not shown]

Figure 5: Overall structure of the study

7.2.2 DSMB Review

Throughout the study, the DSMB will monitor blinded safety measures and demographics at regular intervals as specified in the DSMB charter, or as requested by the DSMB chair. The DSMB will receive reports of adverse events by organ class, with emphasis on SAE’s, clinically significant adverse events with a high causality potential to the study treatment, PEx episodes, and adverse events in the ophthalmological and dermatological class. Members of the DSMB will not be directly involved in the conduct of the study and cannot serve as Investigators in this study.

The DSMB will be composed of:

- Two physicians involved in the care of CF patients, experienced in clinical research, independent of Laurent Pharmaceuticals and not involved as an Investigator on the study.
- One Ophthalmologist experienced in clinical research, independent of Laurent Pharmaceuticals.
- One study biostatistician that can be unblinded with regards to patient randomization, meaning that it is not involved in the statistical design, analysis and reporting of the study.
- Ad-Hoc members recruited to provide specific expertise and meet the Board's mandate.

Each DSMB member will sign a Conflict of Interest Statement which includes current affiliations, if any, with pharmaceutical and biotechnology companies (e.g., stockholder, consultant), and any other relationship that could be perceived as a conflict of interest related to the study and / or associated with commercial interests pertinent to study objectives.

Data will be presented in a blinded manner during the open sessions of the DSMB unless noted otherwise below. At DSMB meetings data and discussion are confidential. Participant identities will not be known to the DSMB members.

Mandate of the DSMB (to be defined in greater detail in the DSMB Charter):

- Review safety information emerging from the study (and any other study of fenretinide). Particular attention will be paid to PEx incidence and due to the profile of fenretinide, ocular and dermatological AEs. Moreover, the DSMB will have access to the randomization code, if justified.
- Meet at specific times of the study to review the safety data cumulated to date. The following specific times have been selected a priori:
 - When a minimum of half of the enrolled patients have completed at least one dosing cycle and corresponding safety information is available, along with Day 21 plasma retinol and retinol binding protein concentration data. This will not be a full unblinding; it will be an unblinded safety analysis of Active versus Placebo;
 - When a minimum of half of the enrolled patients have completed the first 3 dosing cycles and corresponding safety data is available for review. This will not be a full unblinding; it will be an unblinded safety analysis of Active versus Placebo;
 - Outside of the above, every 6 months;
 - Anytime as needed for review of clinically significant safety information brought to the attention of the DSMB.
- Provide guidance to the study team with regards to safety trends. Recommendation to implement a systematic dose reduction or continue the study at the planned dose level will be made by the DSMB and reviewed by the Laurent Pharmaceutical's Team, who will take the final decision to pursue dosing or not (see Sections 7.2.3, 7.2.4 and 8.4.1 for Study/Treatment Arm Stopping Rule Guideline, Treatment Arm Dose Reduction Guideline, and Individual Patient Stopping Rules, respectively).

7.2.3 Study / Treatment Arm Stopping Rule Guideline

The following should serve as a guide for the DSMB to recommend stopping the enrolment and/or further drug administration in a given treatment arm. An agreement will be reached with the DSMB on the guideline prior to the study. Other considerations may be used to arrive at such decisions, which must involve Laurent Pharmaceuticals Executive Management.

- Occurrence of any case of death that may be attributed to fenretinide (in such a case, the blind will have to be broken and allocated treatment identified);
- Occurrence of an increased number, relative to placebo, of unexpected SAEs that could be attributable to the drug (at least *probable* causality relationship) that raise Investigators/DSMB concerns about patients' safety;
- Increased frequency and/or severity of drug-related adverse events, relative to placebo, that in the judgment of the Investigators/DSMB, will result in the advice to discontinue fenretinide treatment.

7.2.4 Treatment Arm Dose Reduction Guideline

The following should serve as a guide for the DSMB to recommend the reduction of the dose in the fenretinide arm from 300 to 200 mg/day. An agreement will be reached with the DSMB on the guideline prior to the study. Other considerations may be used to arrive at such decisions, which must involve Laurent Pharmaceuticals Executive Management.

- Increased frequency and/or severity of drug-related adverse events that in the judgment of the Investigators/DSMB, will result in the advice to reduce the dose of fenretinide treatment.

7.3 Blinding and Randomization

Given the potential for bias in the interpretation of safety and Quality of Life endpoints, as well as the potential for treatment bias that would affect PEx severity and related antibiotic treatment route of administration and duration, among other factors that could potentially bias the trial, the APPLAUD study must be placebo-controlled, double-blinded, and randomized in order to obtain sufficiently robust data.

7.3.1 Rationale for Placebo Control

There is no permanent cure for CF, and the current drug therapies goals are to reduce the symptoms of disease, such as preventing progression of lung infection by removal of the mucus plugging from the lungs, controlling the infection and inflammation, controlling the nutrition level, and ultimately increasing survival. As they are achieving their goals it is therefore appropriate to assess the safety and potential benefit of LAU-7b added to the standard of care for CF patients. A placebo control is suitable and will permit to have unbiased assessment of the several variables. It is essential to maintain the patients on their standard of care, assuming this meets all inclusion/exclusion criteria, as well as allowed vitamin supplements.

7.3.2 Blinding and Breaking the Blind

This is a double-blind study. Patients, Investigators and Site Staff, sponsor and CRO personnel, and data managers will be kept blinded to treatment assignments until the end of the study, except for emergency unblinding as described below. More specifically, to ensure the blinding is maintained when there are no safety concerns requiring unblinding, pharmacokinetic data, pharmacodynamic biomarker results, including post-screening plasma retinol and retinol-binding protein, will not be communicated back to blinded staff.

Only the Clinical Trial Material manufacturer's and Packaging/Distribution provider's unblinded staff and CRO staff administering the interactive web response system (IWRS) will be knowledgeable of individual treatment assignments. As well, in the case of emergency unblinding as described below, some additional people will become aware of treatment assignment for specific patient(s).

The study blind may be broken for an individual patient or several patients in the event of an emergency in which knowledge of the treatment assignment is needed for the safety of the patient(s) and/or for medical decision-making or as required by local regulatory authority. Unless the event for which the blind needs breaking is life threatening, the investigator should first contact the CRO's medical monitor (or designee) prior to breaking the blind. The investigator will obtain unblinding information from the staff administering the IWRS in the form of IWRS access and sealed randomization envelopes. The reason and justification for breaking the blind must be fully documented in the source documentation and captured on the patient(s) electronic case report form (e-CRF). Additionally, all SAE, as they are received but in respect of the reporting requirements enunciated in the DSMB charter, will be referred to the chair of the DSMB, who may request unblinding of the patient, and may call an *ad hoc* meeting of the DSMB to review the data relevant to the study stopping/dose reduction guidelines.

7.3.3 Randomization Scheme and Stratification

Computer-generated randomization sequences will be programmed into the IWRS. At the time of Randomization during Visit 2, not before, the IWRS will assign a randomization number to each patient.

Randomization will be stratified by

- 1- FEV₁ severity collected at the Screening Period (<70% versus ≥70% predicted);
- 2- Number of PEx (all PEx episodes, whether treated by oral or IV antibiotics): ≤3 versus > 3 PEx episodes in prior year; and
- 3- Co-administration or not of Kalydeco® (ivacaftor), Orkambi® (ivacaftor/lumacaftor), Symdeko® (ivacaftor/tezacaftor) or another commercially available CFTR modulator product.

Once stratified, patients will be randomized in a 1:1 double-blinded fashion to either LAU-7b (active) group or the placebo (control) group. Stratification will enable an even distribution of severity and key baseline characteristics among the two treatment groups.

Detailed instructions for randomization will be provided separately.

8 SELECTION AND WITHDRAWAL OF PATIENTS

8.1 Screening Inclusion Criteria

Patients may be enrolled in and randomized to the study only if they meet all of the following criteria at screening:

1. Signed Informed Consent;
2. Adult men and women (as per State or Province laws) and 18 years and older;
3. Diagnosis of cystic fibrosis (positive sweat chloride test) or confirmation (can be historical) of two genetic mutations (one mutation on each of the two alleles of the CFTR gene) causing CF;
4. Screening FEV₁ between 40% and 100% predicted value for age, gender and height, in patients capable of properly performing the test, and baseline FEV₁ within 15% of the screening value, indicative of stable pulmonary function at entry;
5. History of pulmonary exacerbation, defined as at least one (1) pulmonary exacerbation in the 12 months prior to Screening which resulted in documented IV or oral antibiotic treatment;
6. Clinically stable patients, i.e. patients that had no change in their standard antibiotic medication within 5 weeks prior to randomization, of which 2 weeks minimum are prior to Screening;
7. Patients are eligible independently of their history of pulmonary *PsA* infection and their *PsA* status at screening. Medical charts will be reviewed for the *PsA* history in the 12 months prior to screening;
8. If taking Kalydeco® (ivacaftor), Orkambi® (ivacaftor/lumacaftor), Symdeko® (ivacaftor/tezacaftor) or another commercially available CFTR modulator product, patients must be taking it for a minimum of 3 months prior to screening if naïve to CFTR modulators and 1 month if switched from another CFTR modulator product, and deemed to tolerate it;
9. All patients, whether prescribed pancreatic enzyme replacement therapy or not, are eligible. However, modifications of the dosing regime during the study should be avoided;
10. No change in CF and allowed systemic chronic therapy for a minimum of 5 weeks prior to randomization, of which 2 weeks minimum are prior to screening. Changes in non-CF therapy may be allowed during this period, on a case-by-case basis, after consultation with Laurent Pharmaceuticals. Allowed concomitant diseases and treatment are listed in specific section;
11. Female patients of child bearing potential should be on a highly effective contraceptive method during the study, such as hormonal contraceptives, intrauterine device or tubal ligation. Women of childbearing potential are defined as any female who has experienced menarche and who is NOT permanently sterile or postmenopausal. Postmenopausal is defined as 12 consecutive months with no menses without an alternative medical cause. In addition, since the potential of fenretinide to reduce the effectiveness of oral contraceptives has not been established, such patients will be required to use a second contraceptive method such as a barrier method. The contraceptive methods will all be continued for a minimum of a month after the last dose of study treatment. Periodical abstinence, calendar based methods and withdrawal are not considered effective methods of contraception;
12. Male patients with spouse or partner of child bearing potential, or pregnant, are eligible if they use an appropriate method of contraception, such as condoms and spermicide, and if their non-pregnant spouse or partner use an appropriate method of contraception such as oral contraceptives or intrauterine device. The contraceptive methods will all be continued for a minimum of a month after the last dose of study treatment. Male patients with documented sterilization are allowed to waive the contraceptive methods;
13. Patients deemed capable of adequate compliance including attending scheduled visits for the duration of the study;
14. The patient must be able to swallow the study drug capsules.

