2 SCHEDULE OF EVENTS

	Screening	Baseline	Telephone contacts	End-Of-Cycle 1	End-Of-Cycle 2 ¹	End-Of-Cycle 3	End-Of-Cycle 4 ¹	End-Of-Cycle 6	Follow-up (End-Of-Study visit)	Start of PEx Visit ²	End of PEx Visit ²
Day number	Days -28 to -1	Day 1	Days 10, 38, 66, 94, 122, 150	Day 21	Day 49	Day 77	Day 105	Day 161	Day 189 (or early termination)	1st day of IV Antibiotic	Last day of IV Antibiotic
Visit number	Visit 1	Visit 2	N/A	Visit 3	Visit 4	Visit 5	Visit 6	Visit 7	Visit 8	N/A	N/A
Verification of ID and age	X										
Informed consent	X										
Confirmation of CF diagnosis	X										
Inclusion/Exclusion criteria	X	X									
Medical History including detailed PEx history and precise dates	X	X									
Concomitant Meds and verification of disallowed medications	X	X	X	X	X	X	X	X			
Weight, Height (screening only) and Body Mass Index	X	X		X		X		X	X	X	X
Complete Physical Examination	X								X		
Focused Physical Examination		X		X		X		X			
Ophthalmological examination ³	X					X			X		
Night Vision Questionnaire	X			X		X		X	X		
Pulmonary Function Testing (at min. FEV1)	X	X		X	X	X	X	X	X	X	X
12-Lead ECG	X			X		X		X	X		
Vital Signs including respiratory rate, oxygen saturation and temperature	X	X		X		X		X	X		
Hematology ⁴	X	X		X	X	X	X	X	X		
Chemistry ⁵	X	X		X	X	X	X	X	X		
Pregnancy Test for women	X (serum)	X (urine)		X (urine)	X (urine)	X (urine)	X (urine)	X (urine)	X (urine)		
Urinalysis ⁶	X	X		X	X	X	X	X	X		
Sputum ⁷	X					X		X			
Cystic Fibrosis Questionnaire-Revised (CFQ-R)		X				X		X	X		
Matouk Disease Score (at selected sites)		X				X		X	X		

	Screening	Baseline	Telephone contacts	End-Of-Cycle 1	End-Of-Cycle 2 ¹	End-Of-Cycle 3	End-Of-Cycle 4 ¹	End-Of-Cycle 6	Follow-up (End-Of-Study visit)	Start of PEx Visit ²	End of PEx Visit ²
Day number	Days -28 to -1	Day 1	Days 10, 38, 66, 94, 122, 150	Day 21	Day 49	Day 77	Day 105	Day 161	Day 189 (or early termination)	1st day of IV Antibiotic	Last day of IV Antibiotic
Visit number	Visit 1	Visit 2	N/A	Visit 3	Visit 4	Visit 5	Visit 6	Visit 7	Visit 8	N/A	N/A
Lipidomics (AA, DHA, EPA)		X		X				X	X		
Inflammation and oxidative stress markers, ceramides and metabolipidomic markers		X		X				X			
Systemic bone formation/resorption biomarkers (all patients)		X						X			
Lumbar spine bone density (first 24 patients at selected sites)		X							X		
Randomization		X									
Supervised dosing		X									
Dispensing of study drug packs and drug compliance check where applicable		X		X		X					

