12. Eligibility-defining laboratory tests including at a minimum, urinalysis (dipstick), hematology, serum chemistry, plasma retinol and retinol-binding protein, and pregnancy test if applicable;
13. A Night Vision Questionnaire will be self-administered;
14. Complete ophthalmological examination (includes examination of visual acuity, examination for amblyopia, examination of eyelids, conjunctiva, cornea, pupillary reactions to light and accommodation, low contrast visual function (Contrast Sensitivity), specific dark adaptation tests (see note in Section 11.5), lens, vitreous humor, fundus examination of retina and retinal vessels, fundus visualization of optic nerve and macula), will also serve as the baseline exam;
15. Sputum will be induced using hypertonic saline for the assessment of the CFU for *PsA*. Patients with known intolerance to hypertonic saline will not undergo the procedure, as judged by their treating physician. A precise set of instructions will be provided and applied across sites to minimize sampling variations and ensure sputum sample quality;
16. Screening may be split into more than one visit and all results must be available prior to randomization so that the study Investigator can determine eligibility and schedule the baseline visit.

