9.2.4 Telephone contacts (around Days 10, 38, 66, 94, 122 and 150)

All patients will be contacted by phone on or about 10 days post-first dose of each cycle, to inquire about potential adverse events. Specific attention will be put on probing about adverse events related to visual disturbances or dermatological problems as follows: "How is your vision since the last visit/phone call?" and "How is your skin since the last visit/phone call?" Actions may be taken if necessary.

9.2.5 End-of-Cycle Visits (Visits 4, 5, 6 and 7, on Days 21(window: Days 21-22), 49(window: Days 49-51), 77(window: Days 77-79), 105 (window: Days 105-107) and 161(window: Days 161-163)

Special attention will be put on reports of symptoms/signs of pulmonary exacerbation by patients as this may trigger a set of additional assessments. Details are presented in Section 9.3 "Pulmonary Exacerbation Reporting and Evaluation". Adverse events will be monitored and captured at all visits.

1. **On Days 21, 77 and 161 visits**, the following assessments will also be done:
 - a. Focused physical examination;
 - b. Ophthalmological evaluation: The NVQ will be self-administered, and if Grade 2 severity criteria is met or exceeded (On Day 77 visit, the ophthalmological examination is planned, independently of the NVQ result), a full ophthalmological examination will be performed (includes dark adaptation tests), and if clinically indicated by the ophthalmologist, an electroretinogram will also be performed, in order to evaluate any potential ophthalmological condition developed during the treatment cycle);
 - c. Vital signs and 12-lead ECG;
 - d. Pulmonary function tests (FEV₁);
 - e. Pre-dose blood sampling and urine collection for safety laboratory tests, pregnancy test if applicable, plasma retinol and retinol-binding protein;
 - f. Study drug compliance check and concomitant medications;
 - g. Body weight, with BMI calculated.
2. **On Days 49 and 105 visits**, the following assessments will also be done;
 - a. Safety laboratory tests;
 - b. Pulmonary function test (FEV₁);
 - c. Concomitant medications.
3. **On Days 21 and 77 visits only**: All patients will return prior treatment boxes, for accountability purposes and will receive re-supply of study treatment for their next treatment cycle(s);

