- Pregnancy (β -human chorionic gonadotropin) tests for females of childbearing potential: Serum or urine samples will be obtained as specified in the Schedule of Events, page 10 and analyzed at the central laboratory (serum) or locally (urine). The urine pregnancy test on Day 1 must be negative before the first dose of study drug. A positive result during the study will result in immediate interruption of study drug.
- Follicle-stimulating hormone (FSH; Screening Period only): Blood sample for FSH will be measured for any suspected postmenopausal female with at least 12 months of continuous spontaneous amenorrhea. Serum FSH levels must be ≥ 40 mIU/mL to be considered postmenopausal.
- Plasma retinol and retinol binding protein: while this is to support an exploratory correlation with ophthalmological assessments, measurements may be used to support decisions made in relation with ophthalmological TEAe. Abnormal values may result in ad-hoc follow-up determinations, when associated with ophthalmological TEAe. Post-screening results will not be communicated to blinded staff, in order to maintain the study blind, unless required for emergency reasons.

Finally, clinical laboratory evaluations may be performed at other times if judged to be clinically appropriate by the Investigator.

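### Protocol 8.1 and 11.2 define postmenopausal differently, so a woman with 12 months of unexplained amenorrhea and FSH below 40 mIU/mL escapes the contraception criterion under 8.1 only

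*Protocol*

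**What the plan says.** **Who must use contraception.** Protocol 8.1 item 11 places the requirement on women of childbearing potential and says who they are: "Women of childbearing potential are defined as any female who has experienced menarche and who is NOT permanently sterile or postmenopausal". It then settles the menopausal part: "Postmenopausal is defined as 12 consecutive months with no menses without an alternative medical cause". No laboratory value is mentioned. The synopsis and SAP 2.7.1 item 11 carry the same definition.

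**FSH.** Protocol 11.2 starts from women who already have the 12 months: "Blood sample for FSH will be measured for any suspected postmenopausal female with at least 12 months of continuous spontaneous amenorrhea". It continues: "Serum FSH levels must be ≥ 40 mIU/mL to be considered postmenopausal". The sentence that introduces this group of tests says they are performed in line with the Schedule of Events. Neither the Schedule in protocol section 2 nor the flow chart in SAP 2.4 has an FSH row. The screening list in 9.2.1 item 12 reads "Eligibility-defining laboratory tests including at a minimum, urinalysis (dipstick), hematology, serum chemistry, plasma retinol and retinol-binding protein, and pregnancy test if applicable". Table 1 in 11.2 does not contain FSH either.

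**Pregnancy tests.** The Schedule row "Pregnancy Test for women" shows serum at screening and urine at Days 1, 21, 49, 77, 105, 161 and 189. Section 11.2 refers to the Schedule for when these samples are taken. In the visit narrative, 9.2.5 item 1e (Days 21, 77 and 161) names the test: "Pre-dose blood sampling and urine collection for safety laboratory tests, pregnancy test if applicable, plasma retinol and retinol-binding protein". Item 2, which begins "On Days 49 and 105 visits", lists only safety laboratory work, spirometry and a concomitant-medication check.

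**The concern.** One term, postmenopausal, decides whether an inclusion criterion on contraception applies, and the protocol gives it two meanings. A site that reads 8.1 can enroll a woman without contraception whom a site reading 11.2 would treat as of childbearing potential. The approximately 35-40 planned centers could resolve this differently.

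The protocol itself supplies the reason to care. Section 8.2 item 1 excludes pregnancy because of the potential teratogenic effects of retinoids, and section 5.4.3.2 reports that fenretinide at 800 mg/kg/day was teratogenic in rats and rabbits. Section 8.1 item 11 adds that any effect of the drug on oral contraceptives is not established. Section 11.2 makes a positive pregnancy test a trigger for immediate interruption of study drug, so a missed test delays that step.

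**Working it through.** There is no planned figure to reproduce. The main point is settled by comparing the texts, and the minor point by counting days.

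**Step 1. Classify women under each section.** All are past menarche and not permanently sterile.

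| Case | 8.1 item 11 | 11.2 | Agree? |
|---|---|---|---|
| Less than 12 months without menses | not postmenopausal | FSH step not reached; not postmenopausal | yes |
| At least 12 months, unexplained, FSH at or above 40 mIU/mL | postmenopausal | postmenopausal | yes |
| At least 12 months, unexplained, FSH below 40 mIU/mL | postmenopausal, contraception criterion does not apply | not postmenopausal, so of childbearing potential | **no** |

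The sections disagree in the third row only.

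**Step 2. Would FSH be drawn?** Section 11.2 requires it at screening. Four places from which a site might build its screening worksheet do not name it: the protocol Schedule, the SAP flow chart, 9.2.1 item 12 and Table 1. If it is not drawn, 11.2 is not followed, and the only test applied is the one in 8.1.

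**Step 3. Pregnancy tests at Days 49 and 105.** The phrase for safety laboratory tests in 9.2.5 item 2 does not supply the missing test: item 1e names the pregnancy test separately from safety laboratory tests, and the Table 1 panels (chemistry, hematology, urinalysis) do not include it.

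Inputs: six cycles of 21 days on and 7 days off from Day 1, so cycles 4, 5 and 6 are dosed on Days 85-105, 113-133 and 141-161.

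- Schedule: 6 post-baseline tests (Days 21, 49, 77, 105, 161, 189). Longest interval 161 - 105 = 56 days, covering cycles 5 and 6: 2 × 21 = 42 dosing days.
- Narrative only (9.2.5 and 9.2.6): 4 post-baseline tests (Days 21, 77, 161, 189). Longest interval 161 - 77 = 84 days, covering cycles 4 to 6: 3 × 21 = 63 dosing days.
- Difference: 6 - 4 = 2 tests, and 84 - 56 = 28 more days in the longest interval.

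**The case against.** The strongest reply on FSH is that the two sections can be applied together. Section 11.2 begins with the same 12 months and adds a confirmation, so a site following the whole protocol applies both. The clause in 8.1 about an alternative medical cause might also be thought to leave room for such a check. This is a fair account of what may have been intended, but 8.1 presents its wording as the definition, does not mention FSH and does not refer to 11.2. The list in 9.2.1 item 12 is a stated minimum, so leaving FSH out contradicts nothing. The missing Schedule row is weak evidence alone, since CF genotyping stands under the same introduction in 11.2 and has no row of its own. SAP 2.7.1 belongs to a protocol summary and does not direct sites. These replies reduce the supporting points to a risk of oversight. They do not remove the conflict for a woman below the threshold.

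Three stronger readings are tempting, and the documents do not support them.

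- *Every woman with 12 months of amenorrhea is affected.* A woman at or above 40 mIU/mL is postmenopausal under both sections.
- *Section 8.1 also exempts her from pregnancy testing.* Item 11 deals with contraception only. Testing is governed by 11.2, which limits it to women of childbearing potential and carries the FSH condition, and by a Schedule row addressed to women without that limit.
- *The protocol has two pregnancy-test schedules, one with an 84-day gap.* Section 9.2.5 item 2 is silent and does not cancel the test. The Schedule marks it, 11.2 defers to the Schedule, and 9.5 expects procedures within the Schedule's windows. The 84 days arise only if a site works from 9.2.5 alone.

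**Conclusion.** The conflict between 8.1 item 11 and 11.2 is real and lies in current text. It changes the classification of one group: women with at least 12 months of unexplained amenorrhea and FSH below 40 mIU/mL. For them it decides whether the contraception criterion applies. The documents give no count of such women. That the number is small is an assumption, and no rate is offered. The sample size, the primary endpoint and the analyses are unaffected, so this is a matter of participant safety and uniform site conduct. It should be corrected because the protocol itself states a teratogenic risk.

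The Day 49 and Day 105 point is a minor consistency matter: an incomplete visit list with the governing rule stated elsewhere. Its size, 84 against 56 days and 2 of 6 post-baseline tests, assumes a site that follows only the narrative.

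**What to change.** 1. Reconcile 8.1 item 11, with its copies in the synopsis and SAP 2.7.1, and 11.2, so that a single definition of postmenopausal decides who needs contraception and who needs pregnancy tests. Which definition is kept is for the sponsor's medical team.
2. Make the Schedule of Events (protocol section 2 and its SAP copy) and 9.2.1 item 12 match the definition that is kept.
3. Reconcile 9.2.5 item 2 with the Schedule's pregnancy-test row for Days 49 and 105.

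The cost is protocol and SAP wording. FSH and the Day 49 and 105 urine tests are each already called for somewhere in the protocol, so the reconciliation need not add a procedure.
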